7.4.3 Exploratory analysis

Incidence of TDF resistance substitutions such as mutation change, drug resistance test results will be summarized in patients with unsatisfied virological response, viral breakthrough, or discontinued treatment with HBV DNA ≥ 20 IU/mL.

Univariate and multivariate analysis by logistic regression model will be performed to identify baseline or on-treatment risk factors associated with HCC and disease progression, if applicable. The factors will include gender, age, genotype, baseline HBV DNA category (≥ 2000 or < 2000, IU/mL), baseline HBeAg sero-status, baseline ALT value, baseline LSM value, Week 24 treatment response, Week 48 treatment response. Treatment response is defined as serum HBV DNA < 20 IU/mL. Multivariate analysis will include sex, age and the factors with P ≤ 0.20 in univariate analysis.

Time to HCC/disease progression will be analyzed by cox model. Univariate will be conducted to include all above factors and the selection of multivariate analysis will follow the same rule.

Impact of HBV DNA and virologic response on change of LSM will be summarized by shift table

of descriptive statistics as the mean, standard deviation, minimum, median, maximum, and the number of observations.

The mean changes and percent of the changes of liver stiffness measurement in each visit will be summarized by descriptive statistics as the mean, standard deviation, minimum, median, maximum, and the number of observations for patients with advanced fibrosis and compensated cirrhosis. Compensated cirrhosis is defined as $LSM \geq 12.0$ Kpa ($ALT \leq ULN$) or $LSM \geq 17.5$ Kpa ($ALT > ULN$); advanced fibrosis is defined as 9.0 Kpa $\leq LSM < 12.0$ Kpa ($ALT \leq ULN$) or 12.4 Kpa $\leq LSM < 17.5$ Kpa ($ALT > ULN$).

Time to improvement of fibrosis will be analyzed by cox regression. Improvement of fibrosis is defined as at least 30% decrease of LSM compared with baseline. Univariate analysis will include gender, age, genotype, baseline HBV DNA category (≥ 2000 or < 2000 , IU/mL), baseline HBeAg sero-status, baseline ALT value, Week 24 treatment response, Week 48 treatment response. Treatment response is defined as serum HBV DNA < 20 IU/mL. Multivariate analysis will include sex, age and the factors with $P \leq 0.20$ in univariate analysis.

The relationship between baseline variables or on-treatment variables and improvement of fibrosis will be analysis by univariate and multivariate logistic model. Univariate analysis will include gender, age, BMI category (< 25 or ≥ 25 kg/m²), baseline HBV DNA (≥ 2000 or < 2000 , IU/mL), baseline HBeAg sero-status, baseline ALT value, baseline LSM value, baseline total bilirubin, HBeAg loss at Week 24, treatment response at Week 24 and Week 48, ALT normalized or not at Week 24 and Week 48, change from baseline of LSM at Week 12 and Week 24, change from baseline of GGT at Week 24. Multivariate analysis will include sex, age and the factors with $P \leq 0.20$ in univariate analysis.

Proportion of LSM improvement will be summarized at Week48, Week96, Week144, Week192 and Week240 for patients with baseline LSM result in following groups: LSM improved (LSM decreased from baseline $\geq 30\%$), LSM stable (LSM decreased from baseline $< 30\%$ or no change from baseline), and LSM deteriorate (LSM increase from baseline).

Proportion of fibrosis stage improvement will be summarized at Week 48, Week 96, Week 144, Week 192 and Week 240 for patients of fibrosis stage measured by fibrosis improved from baseline, ≥ 2 stage fibrosis stage improved from baseline, ≥ 1 stage fibrosis stage, no change from baseline, fibrosis stage increase from baseline.

Analyses of correlation coefficients between LSM and ALT level will be analyzed by Pearson correlation coefficients and P-value during every 48 weeks by patients with ALT normal at baseline, patients with abnormal at baseline and overall.

Correlation coefficients between variables change at Week 12 and 24 and LSM change at Week 240 will be analyzed by correlation coefficients and P-value. The change from baseline of Gamma-Glutamyltransferase (GGT), Total Bilirubin (TBIL), Albumin (ALB), International Normalized Ratio (INR) and LSM will be included in the analysis of correlation coefficients at Week 12, platelets (PLT), GPR, APRI, FIB-4 and all the variables included at Week 12 will be included in the analysis of correlation coefficients at Week 24.

A 5-years predicted HCC risks by REACH-B model (see Section 8.5) and observed HCC risks (cumulative incidence of HCC) at Week 240 will be presented in table. Decline in LSM from baseline to Week 240 by visit will be analyzed by a line plot.

In addition, a listing of HBV DNA result will be provided for the following patients:

- Patients with virological breakthrough (defined as 1 log increase in HBV DNA from nadir determined by two sequential HBV DNA measurements).
- Patients with unsatisfied virological response: defined as subjects have HBV DNA ≥ 200 IU/ml at week 48 and afterwards have $\leq 1 \log_{10}$ IU/mL decrease in HBV DNA at two consecutive visits, confirmed by a third visit at least one month apart.

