### 6.2.8. Resistance Surveillance

To evaluate the resistance (if identified) rate, genotypic analysis of the HBV polymerase gene will be performed on storage serum at times outlined in Table 1 using a central laboratory in the following situations:

- Subjects with HBV DNA  $\geq 20$  IU/mL at their last visit. (i.e. week 240 or last visit before withdrawal)
- Subjects with virological breakthrough, defined as HBV DNA level increase  $\geq 1$   $\log_{10}$  IU/mL above the treatment nadir (confirmed on two consecutive visits at least 1 month apart).
- Subjects have HBV DNA  $\geq 200$  IU/mL at week 48 and afterwards have  $\leq$  one log decrease in HBV DNA at two consecutive visits, confirmed by a third visit at least one month apart.

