5.3 Exploratory endpoints

- Incidence of TDF resistance substitutions (if identified) at Week 48, Week 96, Week 144, Week 192 and Week 240
- Baseline or on-treatment risk factors for HCC/disease progression (e.g. gender, age, HBV DNA, genotype, HBeAg sero-status, ALT, platelets, treatment response, etc.)
- Impact of HBV DNA and virologic response on change of liver stiffness measurement (LSM).
- The mean changes of LSM by visit.

- Time to improvement of fibrosis.
- The Relationship between baseline variables or on-treatment variables and improvement of fibrosis.
- Proportion of LSM improvement and of fibrosis stage improvement.
- Analyses of correlation coefficients between LSM and ALT level.
- Correlation coefficients between variables change at Week 12 and 24 and LSM change at Week240.
- Predicted and observed HCC risks at week 240 by REACH-B model.
- Decline in LSM from baseline to Week 240.
- Mean estimated glomerular filtration rate (eGFR) over time by baseline eGFR, mean creatinine clearance rate (Ccr) over time by baseline Ccr, mean serum phosphorus over time.
- Change of average LSM/ALT by visit, change of average LSM by visit, change of median of LSM by visit, change of average GPR APRI FIB-4 by visit, change of median of GPR APRI FIB-4 by visit, change of fibrosis stage by visit.

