Table	4.7.3	The Proportion of Subjects Achieving HBsAg Loss and HBsAg Seroconversion at Week 48, 96, 144, 192 and 240 for Subjects with Negative HBeAg at Baseline - mITT
Table	4.8.1	Change from Baseline for the log ₁₀ IU/mL in Serum HBV DNA by Visit - mITT
Table	4.9.1	Incidence of Subjects Who Experience Viral Breakthrough by Visit - mITT
Table	4.9.3	Incidence of Subjects With Unsatisfied Response by Visit - mITT
Table	4.10.1	The Proportion of Subjects with Histological Improvement - mITT
Table	4.11.1	The Proportion of Subjects with Cirrhosis Reversal - mITT

Table	4.12.1	The Mean Changes of Liver Stiffness Measurement by Visit - mITT
Table	4.12.3.1.1	Shift from Baseline in Fibrosis Stage for Patients with Baseline ALT > ULN - mITT
Table	4.12.3.2.1	Shift from Baseline in Fibrosis Stage for Patients with Baseline ALT ≤ ULN - mITT
Table	4.12.3.3	Shift from Baseline in Fibrosis Stage - mITT
Table	4.13.1	Incidence of TDF Resistance Substitutions - mITT
Table	4.14.1	The Relationship Between Baseline Variables or On-treatment Variables and Newly Diagnosed Hepatocellular Carcinoma (HCC) - mITT
Table	4.14.3	The Relationship Between Baseline Variables or On-treatment Variables and Disease Progression - mITT
Table	4.17.1	Cox Regression Analysis for Time to Newly Diagnosed Hepatocellular Carcinoma (HCC) - mITT
Table	4.17.3	Cox Regression Analysis for Time to Disease Progression - mITT
Table	4.18.1	Impact of HBV DNA and Virologic Response on Change of LSM - mITT
Table	4.18.3	The Mean Changes of Liver Stiffness Measurement by Visit for Patients with Advanced Fibrosis and Compensated Cirrhosis - mITT
Table	4.18.3.1	The % Changes of Liver Stiffness from baseline by Visit for Patients with Advanced Fibrosis and Compensated Cirrhosis - mITT
Table	4.19.7	Cox Regression Analysis for Time to Improvement of Fibrosis - mITT
Table	4.20.3	The Relationship Between Baseline Variables or On-treatment Variables and Improvement of Fibrosis - mITT
Table	4.21.1	Proportion of LSM Improvement - mITT
Table	4.21.3	Proportion of LSM Stage Improvement - mITT
Table	4.22.1	Analyses of correlation coefficients between LSM and ALT level - mITT
Table	4.23.1	Analyses of correlation coefficients between Variables Change at Week 12 and 24 and LSM Change at Week240 - mITT
Table	4.24.1	Predicted and Observed Risk of HCC at Week240 - mITT
Table	5.3.4	Mean values in Non-invasive fibrosis - SA
Table	5.1.1	Overall Summary of Adverse Events - SA

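### Read naturally, the resistance summary in SAP 7.4.3 leaves out some completers with HBV DNA of 20 IU/mL or more at Week 240, whom protocol 6.2.8 requires to be genotyped

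*SAP*

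**What the plan says.** Protocol 6.2.8 (Resistance Surveillance) lists three situations in which the HBV polymerase gene is analysed:

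- HBV DNA of 20 IU/mL or more "at their last visit. (i.e. week 240 or last visit before withdrawal";
- breakthrough: "Subjects with virological breakthrough, defined as HBV DNA level increase" of at least 1 log10 IU/mL above nadir, confirmed;
- HBV DNA of 200 IU/mL or more at Week 48, followed by no more than a one-log "decrease in HBV DNA at two consecutive visits, confirmed by a third visit at least one month apart".

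Table 1 of the protocol schedules genotypic analysis at Week 240, and its footnote refers back to 6.2.8 for who is tested.

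SAP 5.3 keeps the endpoint at five time points, the last being Week 240: "Incidence of TDF resistance substitutions (if identified) at Week 48, Week 96, Week 144, Week 192 and Week 240". SAP 7.4.3 then sets the group to be reported. Resistance results "will be summarized in patients with unsatisfied virological response, viral breakthrough, or discontinued treatment with HBV DNA" of 20 IU/mL or more. The last of these groups, those who "discontinued treatment with HBV DNA" at or above that level, is the one at issue. In SAP section 9 the corresponding output is Table 4.13.1, "Incidence of TDF Resistance Substitutions - mITT".

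**The concern.** Two of the three groups carry over from the protocol to the SAP. The remaining one changes. The protocol asks whether the subject was viraemic at the last visit, whether that visit was Week 240 or came before withdrawal. The SAP asks whether the subject discontinued treatment while viraemic. The explicit mention of Week 240 has gone, and the SAP gives no reason.

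A completer who is viraemic at Week 240 and meets neither other criterion is then sequenced under the protocol but has no stated place in the SAP summary. The gap falls on the final time point of the endpoint. A report that no resistance was found at Week 240 would rest on fewer subjects than the protocol sets out to test.

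**Working it through.** There is no planned figure to reproduce: neither document states an expected resistance rate, a number to be tested, or a number viraemic at Week 240. The check is a comparison of text, followed by a sizing under stated assumptions.

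**Step 1. Side by side.**

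| Group | Protocol 6.2.8 (tested) | SAP 7.4.3 (summarised) |
|---|---|---|
| Breakthrough | yes | yes |
| Unsatisfactory response | yes | yes |
| HBV DNA ≥ 20 IU/mL at the last visit before withdrawal | yes | yes, as discontinued treatment |
| HBV DNA ≥ 20 IU/mL at Week 240, completer | yes, named | not named |

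**Step 2. Does *discontinued* cover completers?** SAP 7.1 counts subjects who completed separately from those who discontinued early, and its reasons for discontinuation do not include completion. Protocol 5.1.2 also sets the Week 240 visit apart from an early drug discontinuation visit. The natural reading is that completers are outside the phrase.

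**Step 3. Do the other two groups bring them back?** Only in part.

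- SAP 6.2 sets undetectable HBV DNA to 20 IU/mL. From that floor, a rise of 1 log10 needs 20 × 10 = 200 IU/mL. A subject with an undetectable nadir and 20 to 199 IU/mL at Week 240 is therefore not a breakthrough on that value.
- Unsatisfactory response requires 200 IU/mL or more at Week 48. A subject below that level at Week 48 cannot qualify.
- A completer with a rise of 1 log10 or more at Week 240 can still enter, because the breakthrough definition in SAP 7.4.2.3 accepts the last on-treatment measurement.

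The subjects at issue are thus viraemic completers who never met either criterion.

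**Step 4. Does another part of the SAP restore them?** Table 4.13.1 and the mutation listing (Listing 4.2.3) are titled mITT, but a title does not redefine the set that 7.4.3 names for the summary.

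**Step 5. Size, under assumption.** Planned completers: 158 (protocol 4.1). Let f be the assumed proportion of completers with HBV DNA ≥ 20 IU/mL at Week 240. The ceiling on the number omitted is 158 × f.

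| f (assumed) | 158 × f | Subjects, at most |
|---|---|---|
| 1% | 1.58 | 2 |
| 2% | 3.16 | 3 |
| 5% | 7.9 | 8 |
| 10% | 15.8 | 16 |

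The true number is lower by however many of these subjects met breakthrough or unsatisfactory response.

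If viraemia were equally common in completers and in the 186 − 158 = 28 planned dropouts, completers would make up 158/186 = 85% of the protocol's last-visit group.

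**Step 6. Direction.** SAP 6.1 makes the analysis set the default denominator unless otherwise specified. SAP 7.4.3 describes a summary within a subgroup, so it is not clear whether the default applies.

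- *mITT denominator.* Leaving out a subject with a substitution lowers the incidence; leaving out one without a substitution changes nothing. If all 186 are dosed, each missed carrier is worth 1/186 = 0.5 percentage points.
- *Tested-subject denominator.* Suppose r of n summarised subjects carry a substitution, and k of m omitted subjects do. The full-set rate is (r + k)/(n + m), which exceeds r/n only if k/m exceeds r/n. The direction is unknown in advance.

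**The case against.** The strongest reply is that *discontinued treatment* is undefined and could include the planned end of treatment. Treatment lasts 240 weeks, no drug is dispensed at the Week 240 visit (protocol 5.1.2), and no post-study medication is provided (protocol 5.7), so every completer stops study drug then. Protocol 6.3.1.3 uses similar wording for subjects who are on no post-study therapy. SAP 7.5.1 separates stopping the drug from leaving the study, so the disposition categories in SAP 7.1 do not strictly define the phrase. The SAP is also to be read with the protocol and with table shells that are in a separate document.

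That reading is possible, and it is why the point is put as what the text naturally says and not as a certain exclusion. It is still the less natural reading, and if it is the intended one, a clarifying phrase is still needed.

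A reader might also infer more than the documents support:

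- *That 8 to 16 tested subjects are lost.* This takes a 5% to 10% viraemia rate that has no source in the documents, and it counts subjects who stay in through the other two groups.
- *That resistance will be understated because late resistance appears in viraemic completers.* Neither document says so. Protocol 1.3.2 reports that no TDF resistance mutations have been identified in viraemic treated subjects, and the direction of any error depends on the denominator.
- *That the data disappear.* Listing 4.2.3 is titled mITT and may well show an omitted subject's mutation. What is at issue is the incidence summary.
- *That the results are already in hand.* The protocol requires the testing, but the documents do not show that it has been done.

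**Conclusion.** The mismatch is real. As naturally read, SAP 7.4.3 omits from the resistance summary a group that protocol 6.2.8 expressly tests: completers viraemic at Week 240 without breakthrough or unsatisfactory response. The Week 240 summary can be incomplete for that reason.

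The size is at most about 2 to 16 subjects, on the assumption that 1% to 10% of 158 completers are viraemic at Week 240. The effect on the reported incidence is downward or nil with an mITT denominator and undetermined with a tested-subject denominator.

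The consequence is minor. The endpoint is exploratory and descriptive in a single-arm study without hypotheses, and the primary and secondary analyses do not depend on it. It merits a wording correction and no more.

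**What to change.** In SAP 7.4.3, replace the discontinuation phrase so that the summarised set matches protocol 6.2.8: virological breakthrough, unsatisfactory response, or HBV DNA of 20 IU/mL or more at Week 240 or at the last visit before withdrawal. State the denominator (mITT or subjects tested) at each of Weeks 48, 96, 144, 192 and 240, and show the number tested alongside.

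When programming the set, apply the 20 IU/mL threshold to the reported result. SAP 6.2 replaces undetectable values with 20 IU/mL, and the substituted value would itself satisfy the criterion.

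The cost is a short SAP edit and matching rows in Table 4.13.1. No sampling or testing is needed beyond what the protocol already requires.

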### 4.2. Inclusion Criteria

Specific information regarding warnings, precautions, contraindications, adverse events, and other pertinent information on the GSK investigational product or other study treatment that may impact subject eligibility is provided in the IB/IB supplement(s) and product label.

Deviations from inclusion criteria are not allowed because they can potentially jeopardise the scientific integrity of the study, regulatory acceptability or subject safety. Therefore, adherence to the criteria as specified in the protocol is essential.

Subjects eligible for enrolment in the study must meet all of the following criteria:

1. Age 18-60 years(inclusive);
2. Presence of HBsAg in serum at screening and for at least 6 months before screening assessment;
3. Serum HBV DNA  $\geq$  2000 IU/mL if HBeAg positive at screening (with or without ALT elevation); or serum HBV DNA  $\geq$  200IU/mL if HBeAg negative at screening (with or without ALT elevation);
4. Pathologically or clinically diagnosed as advanced fibrosis or compensated cirrhosis defined as one of following(a or b) :
  - a. Liver biopsy showing advanced fibrosis or cirrhosis (Ishak score  $\geq$ 4 or Fibrosis stage  $\geq$ S3 by Scheuer Score, or within the previous 6 months before baseline and provided that no treatment likely to improve liver histology has been taken since). The slides must be available for review by an independent histopathologist.
  - b. Clinical diagnosis: liver stiffness measure (LSM)  $>$ 12.4 kpa (ALT  $>$  ULN) or LSM  $>$ 9.0 kpa (ALT  $\leq$ ULN), (See section 6.2.7) plus one of the following:
    - i. Endoscopy-proven gastroesophageal or gastric varices, non-cirrhotic portal hypertension excluded;
    - ii. Abdominal ultrasound or CT found changes indicating cirrhosis, irregular liver surface or nodularity, with/without splenomegaly(depth of spleen  $>$ 4.0cm or spleen length  $>$ 13cm);
    - iii. Blood platelets  $<$ 100  $\times 10^9/L$  (and other causes of thrombocytopenia excluded);

5. Ability to give written informed consent;
6. A female is eligible to enter and participate in this study if she is of:
  - a. non-childbearing potential (i.e., physiologically incapable of becoming pregnant, including any female who is post-menopausal), or

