8. APPENDIX

8.1 Appendix 1: Description of Inclusion/Exclusion Criteria

Seq No	Type	Description
1	Inclusion	Age 18-60 years(inclusive)
2	Inclusion	Presence of HBsAg in serum at screening and for at least 6 months before screening assessment
3	Inclusion	Serum HBV DNA ≥ 2000 IU/mL if HBeAg positive at screening (with or without ALT elevation); or serum HBV DNA ≥ 200 IU/mL if HBeAg negative at screening (with or without ALT elevation)
4	Inclusion	
Pathologically or clinically diagnosed as advanced fibrosis or compensated cirrhosis defined as one of following(a or b) :
 
a. Liver biopsy showing advanced fibrosis or cirrhosis (Ishak score ≥ 4 or Fibrosis stage $\geq S3$ by Scheuer Score, or within the previous 6 months before baseline and provided that no treatment likely to improve liver histology has been taken since). The slides must be available for review by an independent histopathologist.
 
b. Clinical diagnosis: liver stiffness measure (LSM) > 12.4 kpa (ALT $> ULN$) or LSM > 9.0 kpa (ALT $\leq ULN$), plus one of the following:
 
 • Endoscopy-proven gastroesophageal or gastric varices, non-cirrhotic portal hypertension excluded; • Abdominal ultrasound or CT found changes indicating cirrhosis, irregular liver surface or nodularity, with/without splenomegaly(depth of spleen > 4.0 cm or spleen length > 13 cm); • Blood platelets $< 100 \times 10^9/L$ (and other causes of thrombocytopenia excluded);
5	Inclusion	
Ability to give written informed consent
 
A female is eligible to enter and participate in this study if she is of:
 
a. Non-childbearing potential (i.e., physiologically incapable of becoming pregnant, including any female who is post-menopausal), or
 
b. Child-bearing potential, has a negative urine pregnancy test at screening, and agrees to one of the following methods for avoidance of pregnancy during the period of the study and until 30 days after last dose of study medication:

6	Inclusion	
 • Oral contraceptive, either combined or progestogen alone. • Injectable progestogen. • Implants of levonorgestrel. • Oestrogenic vaginal ring. • Percutaneous contraceptive patches. • Intrauterine device (IUD) or intrauterine system (IUS) showing that the

Seq No	Type	Description

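### Baseline HBV DNA is cut at 2000 IU/mL, the HBeAg-positive entry floor, in every exploratory risk model; a continuous log10 term would keep more information and reduce the mixing with HBeAg status

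*SAP*

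**What the plan says.** SAP 7.4.3 fits four sets of models, and each uses the same binary version of baseline viral load (introduced as "baseline HBV DNA category") next to HBeAg status:

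- Logistic models for HCC and disease progression: the factor list contains "baseline HBV DNA category (≥ 2000 or < 2000, IU/mL), baseline HBeAg sero-status, baseline ALT value, baseline LSM value".
- Cox models for time to HCC and disease progression: "Univariate will be conducted to include all above factors and the selection of multivariate analysis will follow the same rule".
- Cox model for time to fibrosis improvement: "baseline HBV DNA category (≥ 2000 or < 2000 , IU/mL), baseline HBeAg sero-status, baseline ALT value, Week 24 treatment response".
- Logistic model for fibrosis improvement: "baseline HBV DNA (≥ 2000 or < 2000 , IU/mL), baseline HBeAg sero-status".

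The multivariable models take sex, age and any factor with univariate P ≤ 0.20.

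Inclusion criterion 3 (Protocol 4.2, repeated in SAP Appendix 1) asks for "Serum HBV DNA ≥ 2000 IU/mL if HBeAg positive at screening (with or without ALT elevation"), or for "serum HBV DNA ≥ 200 IU/mL if HBeAg negative at screening (with or without ALT elevation"). SAP 6.1 defines baseline as the last assessment before first dose, and Protocol Table 1 schedules HBV DNA at both screening and baseline.

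The SAP gives no reason for the cut and no analysis with HBV DNA on a continuous scale. In the HCC and progression models, ALT and LSM enter as values. Protocol 8.3.5.1 names the HBV DNA titre as a candidate factor without a cut.

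**The concern.** The model cut and the HBeAg-positive entry floor are the same number. At screening, no HBeAg-positive subject can be below 2000 IU/mL, so the lower group is a one-log band of HBeAg-negative subjects. Everyone else, across all higher viral loads, is pooled in the other group. Three things follow.

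- A univariate HBV DNA effect compares a wholly HBeAg-negative group with a mixed one, so part of it is an HBeAg effect. That estimate decides whether HBV DNA goes forward.
- Once HBeAg status is in the model, the HBV DNA effect rests essentially on HBeAg-negative subjects alone. Differences in viral load among HBeAg-positive subjects contribute nothing.
- A small lower group carries little information, and with few HCC events it may contain none.

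At stake is the assessment of a named candidate risk factor. Exploring risk factors for HCC and progression is one of the three aims in Protocol 1.2.

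**Working it through.** **The plan's own figures.** Inputs from SAP 3.2: incidence p = 0.05, half-width e = 0.034, z = 1.96, dropout 15%.

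- N = p(1 − p)(z/e)² = 0.05 × 0.95 × (1.96/0.034)² = 157.85, rounded up to 158.
- 158/0.85 = 185.9, rounded up to 186.

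Both reproduce. Expected HCC events are 158 × 0.05 = 7.9, or 186 × 0.05 = 9.3.

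**Information kept by the split.** The documents do not give the share q of subjects below 2000 IU/mL, so q is varied. For a normal covariate with a linear effect, a binary split keeps φ(z_q)²/[q(1 − q)] of the information, where φ is the standard normal density and z_q the q-quantile. At q = 0.10, z_q = −1.282 and φ = 0.1755, so 0.0308/0.09 = 0.34.

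**HCC events in the lower group.** With equal risk in both groups, 158 × q × 0.05 events are expected, and the chance of none is 0.95^(158q). At q = 0.10 that is 0.95^15.8 = 0.45.

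| Share below 2000 | Subjects of 186 | Information kept | Expected HCC events below 2000 (of 158 subjects) | Chance of none |
|---|---|---|---|---|
| 5% | 9.3 | 22% | 0.4 | 67% |
| 10% | 18.6 | 34% | 0.8 | 45% |
| 15% | 27.9 | 43% | 1.2 | 30% |
| 20% | 37.2 | 49% | 1.6 | 20% |
| 25% | 46.5 | 54% | 2.0 | 13% |
| 50% | 93.0 | 64% | 4.0 | 2% |

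The loss passes one half when q falls below about 21% (about 39 of 186).

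**Effect of the entry floors.** The floors make a plain normal distribution doubtful, so log10 HBV DNA was also simulated with both floors imposed. The assumptions were 30 to 70% HBeAg-positive, mean 3.5 to 5.5 in negatives and 5.0 to 6.5 in positives, and SD 1.0 to 1.3. Between 1% and 23% of subjects fell below 2000. The split kept 8 to 42% of the information, or 6 to 35% after adjusting for HBeAg. These ranges are only as good as the assumed means.

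**Dependence on HBeAg status.** Let h be the HBeAg-positive share, with no HBeAg-positive subject below 2000. The HBeAg-positive share is then 0 below the cut and h/(1 − q) above it. The correlation of the two binary factors is r = √{hq/[(1 − h)(1 − q)]}, and the variance inflation factor is 1/(1 − r²). The grid takes h from 30 to 70% and 10 to 50% of HBeAg-negatives below 2000:

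- Lowest r (h = 0.3, q = 0.07): 0.3/0.93 = 32% HBeAg-positive above the cut; r = 0.18; inflation 1.03.
- Middle (h = 0.5, q = 0.10): 0.5/0.90 = 56%; r = 0.33; inflation 1.13.
- Highest r (h = 0.7, q = 0.15): 0.7/0.85 = 82%; r = 0.64; inflation 1.70.

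The HBeAg imbalance in a univariate comparison is thus marked, while the variance penalty in a joint model is modest.

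**The case against.** The best defence is that this is a prespecified cut at an eligibility threshold, in exploratory models, in a study that tests no hypothesis. Four specific objections have force.

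- **Linearity.** The efficiency figures assume a linear effect. The only HCC risk function in the SAP, REACH-B in Appendix 5, rises by HBV DNA band from 0.11648 to 1.31467 to 2.27028 and then falls slightly to 2.09258. A single log10 term could be misspecified. This stands, and is why a linearity check belongs in the fix.
- **Source of the dependence.** It comes from inclusion criterion 3. A continuous term would still have a floor that differs by HBeAg status. This stands: recoding relieves the problem only in part, by using variation in viral load within both HBeAg groups.
- **Screening against baseline.** The floor applies at screening and the factor uses baseline, so a few HBeAg-positive subjects may fall below 2000. This stands as a qualification.
- **Timing.** The SAP is dated February 2021 and already deals with Week 240 visits affected by COVID-19. Recoding a factor that late in an open-label study invites a post-hoc charge. Still reporting the 2000 cut, labelled as such, answers most of that.

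A reader might also infer three stronger things that the documents do not support. One is that the cut discards most of the information. That needs under about 21% of subjects below 2000; at 25 to 50% the loss is 36 to 46%, and the distribution is not given. Another is that HBV DNA and HBeAg cannot be separated. Both main effects remain estimable, with variance inflation of about 1.03 to 1.70 over the range tried, and HBeAg is a candidate in every model. The third is that every model is short of events. The count applies to HCC only. Disease progression includes HCC plus other events, and fibrosis improvement is a fall of at least 30% in LSM. With 8 to 9 events a multivariable HCC model is fragile however HBV DNA is coded, and the SAP makes the logistic analysis conditional on being applicable.

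**Conclusion.** The point holds as a minor improvement. The cut, its match with the HBeAg-positive entry floor and its use in all four sets of models are plain in the documents. The mixing of HBeAg status into the univariate HBV DNA effect follows from them, apart from drift between screening and baseline.

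The size is conditional. Information kept is about 64%, 43% or 34% if 50%, 15% or 10% of subjects are below 2000, under a normal covariate and a linear effect. For HCC only, the chance of no events below 2000 is 45% if 10% of 158 subjects fall there, at 5% incidence and equal risk. If the lower group truly has lower risk, that chance is higher. The 240-week incidence estimates for HCC and disease progression do not use this factor.

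**What to change.** In SAP 7.4.3:

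1. Enter baseline HBV DNA as continuous log10 IU/mL in all logistic and Cox models, univariate and multivariable.
2. Add a simple check for non-linearity where event numbers allow: fibrosis improvement, and possibly disease progression. HCC will have too few events.
3. Keep the 2000 IU/mL cut as a labelled sensitivity analysis.
4. Report the cross-table of baseline HBeAg status by HBV DNA below and at or above 2000, so that readers can see how the lower group is made up.
5. Do not move the 6 log10 IU/mL split from SAP 7.4.2.3 into the models. It serves the virological response tables and would be another dichotomy.

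The cost is a small change of SAP wording and one extra table; the values are already collected and already summarised on the log10 scale. The price is a linearity assumption, which cannot be tested usefully for HCC. The change should be dated and documented before database lock, or labelled as added later if lock has passed.
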